## 5.6 Control Arm

All participants (including the CPAP group) will be counseled regarding healthy lifestyle behaviors including sleep hygiene habits based on national guidelines and recommendations. Sleep hygiene counseling is considered standard care in this patient group, and many mild patients see an improvement in daytime symptoms when following basic sleep hygiene measures such as spending adequate amounts of time in bed.

### 5.6.1 Three day phone call

The control arm will also receive a phone call three days after visit one, to discuss the sleep hygiene behaviors and answer any questions the participant may have. This phone call will be conducted by the Trial Sleep therapist to ensure that all information given to participants is consistent.

## 5.7 Three month follow up visit

At the end of the 3 month study, participants in both arms will be asked to attend their local sleep service for a three month follow up visit. Participants will be asked to complete the same standardised questionnaires as they completed at the baseline visit (as per Section 10), including the participants weight.

Participants in the CPAP arm will be asked to complete an additional questionnaire regarding their experiences with CPAP and their wish to continue using it (*CPAP Questionnaire CRF*).

At this stage the subject's participation in the trial is complete, and participants will revert to routine clinical practice. **Participants using a CPAP as part of the clinical trial who wish to continue with it will be permitted to keep the CPAP.**

**Participating centres will be provided with sufficient number of CPAPs that patients in the control arm will also have the opportunity to use CPAP at the end of the trial if the patient and their care team feel it is the best option for them.**

In order to select an appropriate study length, similar studies were reviewed. CATNAP found a positive treatment effect from a 2 month trial participation period; however we felt that some patients may need slightly longer to adjust to CPAP therapy. Participants were enrolled in the MOSAIC study for six months; however a study endpoint also included vascular risk. A similar RCT reviewing the effects of treatment on mild OSA had follow up appointments at both three months and six months. The data showed no significant differences in quality of life between the three and six month visits. Therefore, 3 months was considered an appropriate trial length for this study.

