**Participants who are unable to tolerate CPAP at least an hour will be excluded from participation in the study.**

Following the one hour CPAP trial, baseline demographics such as gender, age, height, and weight, will be collected, along with basic medical history (*Baseline Demographics Form*). During this visit participants will be asked to complete a series of standardised questionnaires (as per Section 10). These questionnaires will be self-administered, although the staff at the site will be available to assist participants with any queries.

At this point participants will be randomised by use of a computer generated randomisation schedule into one of two arms; the CPAP arm or the control arm. Randomisation with minimisation will be used, based on age, BMI and gender (See *Randomisation Schedule*).

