## 10 Questionnaires

### 10.1 Short Form 36 (SF-36)

The SF-36 questionnaire is a well validated widely used generic health questionnaire. It was developed as a set of standard, easily administered, quality of life questions for use in routine monitoring and assessment of treatment outcomes in adult patients. The SF-36 measures the limitations of a person's quality of life due to poor health on eight scales: physical activity; social activity; physical health problems; bodily pain; mental health; emotional health; vitality (energy and fatigue); and health perceptions. It takes about 5 minutes to complete.

In this study the Energy and Vitality Component of the SF-36 will be used as the primary outcome, and the entire SF-36 will be used as a secondary outcome.

We have chosen to use a study endpoint of the Energy and Vitality dimension of the SF36, as this has consistently shown to be the most sensitive dimension of the SF-36 for measuring quality of life improvements in mild OSA patients.

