#### A note about AASM 2007 and 2012 scoring

It is not exactly known how many participants will move from Mild OSA as per AASM 2007 to Mild OSA as per AASM 2012. Previous studies which have rescored sleep studies with different criteria have been reviewed to assist with predictions. The most relevant study, conducted by Bahamman *et al* found that up to 45% of patients would have not been diagnosed with OSA using AASM 2007 criteria, but were diagnosed when using AASM 2012 criteria. In our study we expect a higher rate of participants who score no OSA with AASM 2007 to be diagnosed with OSA using AASM 2012, because these patients have presented at the sleep clinic with symptoms, and other sleep disorders have been excluded.

**Using data from previous trials to estimate occurrences of OSA, we originally predicted that a minimum of 264 participants are would be needed to be enrolled in this study to have the required 224 participants in the Mild OSA (AASM 2012) group for primary analysis. This also allows for a 10% drop-out rate.**

These estimations were checked both after the pilot phase (n = 20), and after 50% of enrolment was complete, and the planned sample size.

Based on this updated data, we anticipate that 300 participants are needed to be recruited in order to meet the required number (224) in Mild OSA 2012 group for primary outcome analysis.

Recruitment will continue until 224 participants are enrolled in the mild OSA group (as per AASM 2012).

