5.4 Missing Data

The number and percentage of patients with missing data for each outcome measure at each time point will be reported by treatment group. A completed outcome measure refers to a completed questionnaire with a non-missing summary score. Questionnaires where too many questions were left blank, hindering the calculation of one or more summary scores, will be counted as a missing outcome measure for the corresponding endpoint.

The primary analysis uses a mixed-effects repeated measures model, which assumes data is missing at random (MAR) and incorporates all available information from all subjects.

Baseline characteristics will be summarised for those who did and did not complete the SF-36 energy and vitality questions at the 3-month follow-up visit, by treatment group, to describe any characteristics related to missingness that can be observed.

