5.5 Patient Accountability

A CONSORT flowchart will be constructed to summarise the progression of patients through each study stage for each study population, and reasons for drop-out or exclusions at each stage. The flowchart will show the number of patients in each treatment group who (1) met the initial study criteria, (2) were randomly assigned, (3) received intended treatment, (4) completed specified visits, and (5) were analysed for the primary endpoint. The flowchart will present results overall and for each study population (mild OSA per AASM 2012, mild OSA per AASM 2007 and moderate/severe OSA per AASM 2012).

Protocol deviations from will be presented descriptively by treatment group with the number and percent of total deviations for each deviation type. Protocol deviations include:

Missed 3-month visit

Out of window 3-month visit (visit window defined as 90 days + 1 week)

Incomplete or missing SF-36 Energy and Vitality question responses

The numbers (with percentages) of patients completing the study and lost to follow-up (defaulters and withdrawals) over the 3-month period of the study will be presented by treatment group. Additionally, reasons for losses will be summarized.

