6. STATISTICAL SOFTWARE AND QUALITY CONTROL

Day-to-day monitoring of the trial will be carried out by the Oxford Respiratory Trials Unit (ORTU) along with regular data queries and data checks by the trial statisticians.

Data is received by paper Case Report Forms (CRFs) from sites, entered into electronic database by Oxford. Data is held and managed by the ORTU.

All statistical analyses will be generated using SAS® software, version 9.4 or later. Graphics will either be generated using SAS or R software. Statistical analysis will be independently quality checked by a

second statistician to ensure that the SAP has been followed and programming errors are minimized.

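### The month-3 SF-36 is collected only at a clinic visit; a postal or online fallback would recover some missing primary outcomes at little cost

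*Protocol*

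**What the plan says.** Protocol 5.7 describes the month-3 assessment as follows: "participants in both arms will be asked to attend their local sleep service for a three month follow up visit". At that visit, "Participants will be asked to complete the same standardised questionnaires as they completed at the baseline visit". The task table in Protocol 6.2 gives the repeat questionnaires to the local sleep service at Visit 2. Neither document describes completion by post, telephone or online, or a step to chase a missing month-3 form.

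The form itself does not need a clinic. Protocol 5.4.1 says of the baseline set: "These questionnaires will be self-administered", with staff on hand for queries. Protocol 10.1 says of the SF-36: "It takes about 5 minutes to complete". SAP section 6 adds: "Data is received by paper Case Report Forms (CRFs) from sites". SAP 4.10 schedules the SF-36 at baseline and 3 months only.

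On losses, Protocol 11.2.3 says of its first enrolment estimate: "This also allows for a 10% drop-out rate". SAP 4.6 also expects 10% drop-out. SAP 5.5 lists "Missed 3-month visit" among the protocol deviations, with no recovery step. SAP 5.4 describes the primary model as one "which assumes data is missing at random (MAR) and incorporates all available information from all subjects". The SAP amendment (section 8) replaces missing 3-month scores with baseline scores in the sensitivity and secondary analyses.

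**The concern.** The primary endpoint is a patient-reported vitality score with one post-baseline measurement. A patient with only a baseline score informs the baseline mean and variance in the mixed model but adds almost nothing on change. So the model's use of all available data rescues little, and what replaces the missing score is an assumption: missing at random in the primary analysis, no change from baseline in the amended analyses.

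Two things are at stake. One is precision. The other is bias, if the people who miss the visit differ in benefit from those who attend. Collecting the score is better than either assumption, and for someone who has missed a visit but not withdrawn consent, a short paper or online form may be enough.

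**Working it through.** **Inputs.** Mean change 10.8 (SD 17.0) with CPAP and 4.2 (SD 18.1) with standard care, so a difference of 6.6 (Protocol 11.2.1). Two-sided 5%, 80% power (SAP 4.6). 1:1 allocation (SAP 4.2). 10% drop-out from all causes (SAP 4.6). The share of that 10% recoverable by a remote form is not in the documents; 25%, 50% and 75% are assumed.

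**1. The plan's own figure.** n per arm = (1.960 + 0.842)² × (17.0² + 18.1²) / 6.6² = 7.85 × 616.61 / 43.56 = 111.1, rounded up to 112, or 224 in total. This reproduces the stated size. Two-sample t power (noncentral t) at 112 per arm is 80.0%. The 224 contains no drop-out allowance: 224 / 0.9 = 249 would have to be enrolled in the mild OSA (AASM 2012) group.

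**2. Power if 224 are enrolled.** Protocol 11.2.3 continues recruitment until 224 are enrolled in that group. Analysable n = 224 × (1 − 0.10 × (1 − r)), where r is the share recovered.

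| Share recovered (assumed) | Analysable n | Power |
|---|---|---|
| 0% | 202 | 75.7% |
| 25% | 207 | 76.8% |
| 50% | 213 | 77.9% |
| 75% | 218 | 79.0% |
| 100% | 224 | 80.0% |

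**3. Power if 224 complete.** SAP 4.6 aims for 224 completing, so about 249 enrolled and about 25 lost. Recovering 25%, 50% or 75% of the 25 gives about 230, 236 or 242 analysable, and power of 81.0%, 82.0% or about 83%, against 80.0% with none recovered.

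**4. Bias, as an illustration only.** Suppose 10% of CPAP patients are missing and changed like controls (4.2), while the observed CPAP patients changed by 10.8.
- True CPAP mean: 0.9 × 10.8 + 0.1 × 4.2 = 10.14, so the true difference is 10.14 − 4.2 = 5.94.
- An analysis assuming missing at random gives 10.8 − 4.2 = 6.60, which is 0.66 too high.
- With a share r recovered at random, the CPAP mean is (0.9 × 10.8 + 0.1 × r × 4.2) / (0.9 + 0.1 × r). For r = 25%, 50% and 75% the estimated difference is 6.42, 6.25 and 6.09.

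**5. Carried-forward baseline.** If instead the missing patients would have changed like the observed ones (true difference 6.6), setting their change to zero gives 0.9 × 10.8 − 0.9 × 4.2 = 5.94 with 10% missing in both arms, and 0.9 × 10.8 − 4.2 = 5.52 with 10% missing in the CPAP arm only. The two planned methods can therefore err in opposite directions, and recovered scores reduce both errors.

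**The case against.** The strongest reply is that this is an omission, not an error. Nothing forbids remote return, and the ITT-1 primary model would accept a score received that way. The power gain is about 2 points at 50% recovery. If the SAP goal of 224 completers is met, planned power is already there. The 75.7% starting point arises only under the Protocol's enrolled wording, and the conflict between that and the SAP's completing wording has to be reconciled separately. In the bias illustration, 0.66 is about 0.28 of the standard error of the difference (√(616.61 / 112) = 2.35). It also assumes no benefit over control in the missing patients, and that those recovered are a random sample of them. All of this stands and limits the size of the point.

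Several stronger readings are tempting but not supported:
- **That the SAP treats a missed visit as a missing outcome.** SAP 5.5 lists missed visits and missing vitality responses as separate deviations, and SAP 5.4 defines missingness by whether a summary score exists. Late visits are also listed separately, so a late visit can still supply data. Only the completed-case sets in SAP 5.1 depend on the visit.
- **That everything collected at month 3 is a questionnaire.** Weight is also taken then (Protocol 5.7), and its change is an exploratory outcome.
- **That most lost scores could be obtained.** The 10% covers all causes. It includes people who withdraw and CPAP patients withdrawn after failed contact (Protocol 5.5.3).
- **That the arms have different reasons to attend.** Protocol 5.7 offers controls possible CPAP access at the end of the trial and lets CPAP patients keep the device. Only the CPAP arm has continuous monitoring and a withdrawal rule for failed contact. Differential loss is plausible in an open-label trial, but it is not documented.

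**Conclusion.** The point holds as a cheap improvement to the collection method. As written, a short self-administered primary outcome with a single post-baseline time point can be obtained only by clinic attendance, with no fallback or reminder.

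The size is modest: with 224 enrolled, 1.1 to 3.3 points of power for 25% to 75% recovery of the expected 10%; with 224 completing, about 1 to 3 points. Reduced reliance on missing at random and on carried-forward baseline matters more than power, but its size cannot be fixed from the documents. The 6.60 against 5.94 shows scale and is not a forecast. The recovery shares are assumptions, and the split of the 10% by cause is unknown.

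**What to change.** **Protocol 5.7.** If the month-3 visit is missed or cannot be booked within the window, and consent has not been withdrawn, send the questionnaires, SF-36 first, by post or secure online form with one reminder. Apply this in both arms and include patients who have stopped CPAP. Record the mode and date of completion.

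**SAP 5.4, 5.5, 5.7 and 5.8.** State that these scores count as observed month-3 data in the ITT-1 and ITT-2 analyses. Report the numbers by arm and mode. Repeat the primary analysis with clinic-completed scores only.

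**Cost.** Protocol and SAP wording, postage or a form link, one reminder, and a check that consent covers remote contact, which cannot be confirmed from the material available. The Trial Sleep Therapist already telephones both arms at three days (Protocol 5.5.2 and 5.6.1) and site data are on paper, so the extra work is small. The downsides are a possible small mode effect, which the clinic-only analysis would examine, and weight that is missing or self-reported for these patients.

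**Timing.** SAP 4.2 expected follow-up to end on 31 March 2019, before the June 2019 amendment. If follow-up is already complete, what remains is to report, by arm, how many missing month-3 vitality scores were due to a missed visit rather than withdrawal or loss of contact.

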## 5.8 Pilot Phase

In order to test the trial methodology, the trial will start with a pilot phase of 20 randomised participants. At this stage the steering committee will meet to review the following:

- Average CPAP compliance
- Trial methodology and flow

**Compliance to treatment is crucial for study to be able to demonstrate whether CPAP treatment yields improvements in mild patients.** In order for patients to experience quality of life benefits, it has been shown that at least 4 hours usage per night is required, with greater use associated with increased benefits. If, during the pilot phase, average compliance is lower than 4 hours per night, the protocol will be amended to include the use of a CPAP 3 day run in phase, in order to include only patients who are able to use the device for greater than four hours per night. Additional changes to the protocol may also be made based on findings from the pilot phase.

# 6 Study Responsibilities

## 6.1 Terms

**Local Sleep Service** refers to UK based sites which currently screen, diagnose and treat sleep disorders, such as hospital respiratory departments. These sites are those experienced with diagnosing and treating obstructive sleep apnea, as well as initiating CPAP treatment, and will be involved in the screening and set-up of trial participants

**Central Scorer** refers to an expert Central scorer who will review all studies scored using AASM 2012 criteria.

**Trial Sleep Therapist** refers to a specialist with extensive experience initiating CPAP in patients, managing OSA patients, and troubleshooting equipment problems. The Trial Sleep Therapist is part of the trial team (independent from the trial sites), and is centrally located.

## 6.2 Trial Tasks

Task	Timeline	Responsibility
Home Sleep Screening Test	Screening	Local Sleep Service
AASM 2007 scoring (Automatic software scoring)	Screening	Local Sleep Service
Data uploaded to Trial account	Screening	Local Sleep Service
AASM 2012 scoring (Automatic software scoring)	*Occurs at the point of screening if patient has an AHI 0-4 using AASM 2007, otherwise occurs throughout course of study	ResMed

AASM 2012 scoring reviewed by Central Scorer	Throughout course of study	Central Scorer
Visit 1 
 
- Check inclusion (including CPAP tolerance 1 hour test)
 
- Demographics
 
- Questionaries
 
- Randomisation
 
- Sleep hygiene counselling
 
- CPAP initiation (CPAP group only)
 
- Add CPAP details to Trial AirView Account
 
	Visit 1	Local Sleep Service
3 day phone call 
 
- Address questions regarding sleep hygiene counselling
 
- Check on CPAP acceptance (CPAP group only)
 
	3 day phone call	Trial Sleep Therapist
Ongoing wireless monitoring 
 
- Intervene if Compliance is low or other issues are seen
 
- Organise additional visits if required
 
	Continuously throughout 3 month study	Trial Sleep Therapist
Visit 2 (3 month follow up) 
 
- Repeat baseline questionnaires
 
- Additional questionnaire for CPAP group
 
- Trial participation complete, patient continues with routine clinical care
 
	3 month follow up visit	Local Sleep Service

## 7 Selection and Withdrawal of Participants

### 7.1 Inclusion Criteria

In order to be eligible to participate in this study, an individual must meet all the following criteria:

Inclusion Criteria

Study Screening:
 
 
• AHI 5-15 events/hr as per AASM 2007 scoring criteria or AHI <math>\geq 5</math> per AASM 2012 if AHI 0-4 per AASM 2007
 
• Aged <math>\geq 18</math> and <math>\leq 80</math> years
 
• Ability and willingness to provide written informed consent
 
• Ability to tolerate a CPAP one hour long run in test
 

### 7.2 Exclusion Criteria

Exclusion Criteria

 
• The presence of unstable cardiac disease
 
• Inability to give fully informed consent
 
• Supplemental oxygen
 
• Secondary sleep pathology e.g. Periodic Limb Movement Syndrome, Narcolepsy, Circadian Disorder, obesity hypoventilation syndrome suspected or diagnosed at local sleep service
 
• BMI <math>\geq 40</math> Kg/m^2
 
• ESS score at baseline <math>\geq 15</math>, or concerns about sleepy driving from physician/ sleep lab staff
 
• Previous CPAP usage
 

### 7.3 Selection of sites

Study sites (“local sleep services”) are defined as sites which currently screen, diagnose and treat sleep disorders, such as hospital respiratory departments. Eligible sites are those experienced with diagnosing and treating obstructive sleep apnea, as well as initiating CPAP treatment. These factors, as well as the ability of the site to conduct research, will be assessed at the site selection/ site initiation visits. Appropriate Health Research Authority (HRA) and National Health Service (NHS) approval will be obtained for each participating site.

### 7.4 Selection of participants

Potential participants who meet the screening criteria will be identified through U.K. based local sleep services. These patients will be told about the study by their treating clinician at the local sleep service. Those who would like more information will be given the Patient Information Statement. Participation in the trial is voluntary and Informed Consent will be obtained for each participant before their home sleep test is sent for independent review.

### 7.5 Handling of Subject withdrawals

Enrolment is completely voluntary and participants are free to withdraw from the study at any time. Subjects who withdraw will continue to visit their local sleep service for routine clinical care. Reason for withdrawal will be documented on the participants CRF.

### 7.6 Premature Termination or suspension of study

In the unlikely event that the study is terminated or suspended, participants will continue to visit their local sleep service for routine clinical care.

## 8 Expected Duration of the Trial

### 8.1 Duration per participant

The duration for each trial participant is expected to be 13 weeks. 1 week for Apnealink testing and baseline visit, and 12 weeks of CPAP use for the active arm.

### 8.2 Duration of the study

Between 5 and 15 UK centres are expected to take part in the trial. Enrolment is expected to occur at a rate of approximately 2 patients per centre per month. Recruitment and follow up is estimated to take 1.5 years. **The entire study, including analysis and reporting, is anticipated to take approximately 2 years.**

## 9 Trial Devices and Procedures

### 9.1 Apnealink Air Home Sleep Test

Portable Home Sleep Testing devices are widely used in the screening and diagnosis of sleep apnea, and have been validated in many studies. In the screening phase of this trial, the ResMed Apnealink Air device will be used to diagnose sleep disordered breathing in the patient’s home. The Apnealink Air is a commercially available PG device which is small and simple to use. Many sleep services in the UK already use the Apnealink Air for routine screening. It contains software which allows for the

scoring of apneas, hypopnoea and arousals. It is a portable device which consists of a nasal cannula to measure nasal flow and snoring, oximeter to measure pulse and blood oxygen levels, and a chest band to measure respiratory effort.

Participants will be provided with an Apnealink Air from their local sleep service. They will be shown how to use it and instructed to take it home for use. The Apnealink Air contains user feedback which shows if a successful night has been recorded. The device can be re-used up to three nights. Participants will return their Apnealink Air to the sleep clinic either in person or in a replied paid envelope. The device will be downloaded and automatically scored using the electronic software.

If the sleep report shows an AHI  $\leq 15$ , the participants will be asked if they are happy to proceed to the next stage. If the patient provides consent, the Home Sleep Test data will be uploaded to the Trial AirView account for review to assess the participants eligibility to enter the study.

